8.2.2 Other Safety Measures

Concomitant medications and concomitant procedures will be recorded on the Prior and Concomitant eCRF and Concomitant Procedures eCRF, respectively.

Concomitant AED administration since last visit will be recorded on the eCRF page.

Vital signs will be recorded on the Vital Signs eCRF. These data will include blood pressure, heart rate (supine for 5 minutes), temperature, respiratory rate, and weight.

Physical examinations will be recorded on the Physical Exam eCRF. These data will include Body System, normal/abnormal indication, and a description of the abnormality.

Routine 12-lead ECGs will be performed periodically during the study. Parameters including Heart rate, PR interval, QRS interval, RR interval, QT interval, and QTcF will be measured. These results will be recorded on the eCRF.

A brief neurologic evaluation examination will be made and recorded on the eCRF.

Clinical laboratory evaluations will be collected and returned electronically and not entered on an eCRF. Clinical Laboratory Evaluations will include the following:

- Hematology: hemoglobin, hematocrit, white blood count with differential, RBC count, platelet count, and calculated indices.
- Serum chemistry: blood urea nitrogen (BUN), calcium, chloride, creatinine, glucose, total bilirubin, direct bilirubin, alkaline phosphatase, aspartate transaminase (AST), alanine aminotransferase (ALT), total protein, albumin, globulin, sodium, potassium, phosphorus, and glucose. Serum creatinine will be used to calculate the creatinine clearance.
- Urinalysis: pH, specific gravity, protein, glucose, ketone, bilirubin, blood, nitrite, urobilinogen, and microscopic examination
- Pregnancy Tests – All females of child-bearing potential will undergo a serum pregnancy test for β -hCG (β -human chorionic gonadotropin).

All safety laboratory samples will be analyzed by a central laboratory.

The follow-up version of the Columbia Suicide Rating Scale (C-SSRS) will be assessed at Visit 2 and all subsequent visits throughout the study and entered on the eCRF.

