11.5 Prior and Concomitant Medications and Procedures

Baseline AED medications are defined as AED medications that started prior to and are ongoing at the time of the first dose.

Concomitant AED medications are defined as AEDs that started prior to and are ongoing at the time of the first dose of study medication or started after the first dose of study medication.

Prior medications are defined as non-AED medications with a start date and stop date prior to the first dose of study medication.

Concomitant medications are defined as non-AED medications with a start date on or after the first dose of study medication (Day 1) or started prior to and are ongoing at the time of the first dose of study medication.

Concomitant procedures are defined as procedures with a start date on or after the first dose of study medication (Day 1).

Prior and concomitant therapies will be coded to a World Health Organization Drug Dictionary (WHO DD) term including ATC classification (Version March 2016 or a later version available at the time of data cut-off). A by-subject listing of baseline AEDs, concomitant AEDs, prior and concomitant non-AEDs use, and concomitant procedures will be produced.

The use of baseline and concomitant AEDs, prior non-AEDs, and concomitant non-AEDs will be summarized by safety evaluable subgroup and overall for subjects in the safety population. The number and percentage of subjects taking each medication will be presented by ATC Classification.

In addition, a summary table for:

- Number of baseline AEDs (0, 1, 2,->2)
- Number of baseline AEDs per subject (mean, standard deviation, median, minimum, and maximum number of AEDs)

will be prepared for safety population (overall and by safety evaluable subgroups).

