- q. Site calls to subjects at least once in between the clinic visits to remind them to be vigilant regarding signs and symptoms of DRESS
- r. Every 3 months after Visit 14

18 APPENDIX 2: DATA HANDLING RULES FOR MISSING OF PARTIAL START/STOP DATES FOR CONCOMITANT MEDICATIONS, CONCOMITANT AEDS, AND BASELINE AEDS

Concomitant Medications and Concomitant AEDs

If a concomitant medication or AED, as reported on the eCRF, has a partially or completely missing start or end date, use the following algorithm to impute missing components of the date(s). Imputed dates will be used in order to determine prior/concomitant status of a medication.

If a medication has some missing components in both the start and end dates, first impute the end date as follows (only if the medication is not ongoing):

1. If CMENDTC contains only year and month – impute the missing day to the last day of the corresponding month (e.g., 31 for January, or 30 for April) or date of data cut-off (whichever comes first).
2. If CMENDTC contains only year – impute the missing day and month to the 31st of December of the corresponding year or date of data cut-off (whichever comes first).
3. If CMENDTC is completely missing impute to the date of end of the last period/phase defined for the subject or date of data cut-off (whichever comes first).

Note: The end date should remain null for medications that are ongoing.

After having imputed the end date (if needed), impute the therapy start date if it is partial or missing as follows:

4. If CMSTDTC contains only year and month – impute the missing day to the 1st day of the corresponding month.
5. If CMSTDTC contains only year – impute the missing day and month to the 1st of January of the corresponding year.
6. If CMSTDTC is completely missing impute to the date of start of the screening period (of IFC date) or to the medication end date (previously imputed if needed), whichever is earlier.

Baseline AEDs

Baseline AEDs are AEDs that started prior to and are ongoing at the time of the first dose of study medication.

Any AEDs recorded as “prior” in eCRF will be evaluated if it is a baseline AED or not.

- (1) If both start and stop dates are missing, the medication will not be considered as Baseline AEDs and will not be counted in number of baseline AEDs.
- (2) If an AED is identified as Prior in eCRF and it is “not ongoing” and has partial end date, the following rules will be applied:

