 - if CMENDTC contains only year or day -year and year < first dose date year, the medication will not be considered Baseline AED
 - if CMENDTC contains only year or day-year and year >= first dose date year, the medication will be considered Baseline AED
 - if CMENDTC contains only month-year and month-year < first dose date month-year, the medication will not be considered Baseline AED
 - if CMENDTC contains only month-year and month-year >= first dose date month-year, the medication will be considered Baseline AED
 - if CMEDTC contains only day-month (ie, no year), the medication will not be considered Baseline AED
- (3) If AEDs are not recorded as “prior” in eCRF, the following rules will be considered if start dates are missing or have partial dates:
 - If CMSTDTC contains only year and month – impute the missing day is the 1st day of the corresponding month.
 - If CMSTDTC contains only year – impute the missing day and month to the 1st of January of the corresponding year.
 - If CMSTDTC is completely missing impute to the date of start of the screening period (of IFC date).
- (4) After AED start date is imputed:
 - If the imputed start date > the first dose date, AED will not be considered “prior” AED and will not be considered Baseline AED

- If the imputed start date \leq the first dose date, AED will be considered “Prior” AED and will be evaluated as potential Baseline AED. The decision if AED is Baseline AED will be based on CMENDTC [as per rule (2) above].

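### SAP Appendix 2 classes a stopped AED with both dates missing as concomitant but not baseline, a combination that SAP 11.5 does not allow

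*SAP*

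**What the plan says.** SAP Section 11.5 defines a baseline AED as one begun before the first dose of study drug and still being taken then. The first limb of the concomitant definition is the same test: "Concomitant AED medications are defined as AEDs that started prior to and are ongoing at the time of the first dose of study medication". The only other way to be concomitant is to start after the first dose. Both kinds of AED use are summarised by subgroup and overall, and the number of baseline AEDs has its own table.

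Appendix 2 holds two sets of date rules.

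- **General rules 1 to 6** cover concomitant medications and AEDs with a missing or partial start or stop date. Their purpose is stated: "Imputed dates will be used in order to determine prior/concomitant status of a medication". For drugs not marked ongoing, rule 3 says "If CMENDTC is completely missing impute to the date of end of the last period/phase defined for the subject", or to the data cut-off, whichever is earlier. Rule 6 sets a wholly missing start to the start of screening (or consent), or to the stop date if that is earlier.
- **Baseline AED rules (1) to (4)** decide baseline status. Rule (1) excludes an AED with neither date and leaves it out of the baseline count. Rule (2) handles partial stop dates of AEDs that are not ongoing. Its last item is "if CMEDTC contains only day-month (ie, no year), the medication will not be considered Baseline AED". Rules (3) and (4) impute a start date for AEDs not recorded as prior and then return to rule (2) for the decision.

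**The concern.** Two algorithms answer the same question, whether the drug was being taken at first dose. They use different defaults when the stop date is unknown. Where they disagree, the baseline and concomitant AED tables contradict each other for the same subject, and a drug stopped before the study can be counted as taken with YKP3089. The opposite error is also possible: a drug taken at first dose and stopped later, with no dates recorded, is left out of the baseline count. Co-medication matters here because interactions between YKP3089 and other AEDs are among the study objectives and results are presented by AED-defined subgroups.

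**Working it through.** The plan gives no figure to reproduce. The check applies both rule sets to an AED marked not ongoing, for one illustrative subject. The dates are assumed: consent 1 March 2017, first dose 20 March 2017, end of last phase 30 April 2018, data cut-off 1 July 2018. Three start patterns (5 May 2010; 2010 only; missing) were crossed with six stop patterns, giving 3 × 6 = 18 combinations.

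| Start | Stop | General rules: concomitant? | Baseline rules: baseline? | Combinations |
|---|---|---|---|---|
| missing | missing | yes | no, rule (1) | 1 |
| 5 May 2010, or 2010 only | missing | yes, if rule 3 applies | no outcome | 2 |
| any of the three | day and month, no year | no outcome | no, rule (2) | 3 |
| any of the three | 2012 only, or February 2017 | no | no | 6 |
| any of the three | 2017 only, or March 2017 | yes | yes | 6 |

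**Both dates missing.** Rule 3: stop = earlier of 30 April 2018 and 1 July 2018 = 30 April 2018. Rule 6: start = earlier of 1 March 2017 and 30 April 2018 = 1 March 2017. Since 1 March 2017 is before 20 March 2017, and 20 March 2017 is before 30 April 2018, the drug counts as taken at first dose and is concomitant. Baseline rule (1) says it is not baseline. It cannot be rescued as an on-study start, because rule 6 has placed its start before first dose. The result does not depend on the assumed dates: in any dosed subject, screening comes before the first dose, and neither the last phase nor the cut-off ends before it.

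**Known start, stop wholly missing.** Baseline rule (1) does not apply because a start is present. Rule (2) covers only partial stop dates, and rule (4) leads back to rule (2). There is no baseline outcome. Under rule 3 the AED is concomitant.

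**Stop with day and month only.** Baseline rule (2) says not baseline. General rules 1 to 3 cover year with month, year alone, and nothing, so this pattern has no outcome there.

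**Stop year known.** The two sets agree in all 6 + 6 = 12 combinations. The defect is confined to an unknown stop year.

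**Size per record.** Concomitant AEDs are reported as number and percentage of subjects. One record adds at most one subject to a drug's count: 1/20 = 5 percentage points in a phenytoin or phenobarbital subgroup at its planned minimum, and 1/1,000 = 0.1 point against the overall exposure target.

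**The case against.** The strongest reply is that only one pattern gives opposite answers. That is right: the other two are gaps, and the point is put that way here.

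Rule 3 can also be read narrowly. Its sub-heading refers to concomitant drugs, and the lead-in to rules 1 to 3 speaks of components missing in both dates, so a complete start with no stop might never reach it. The opening paragraph, however, covers a missing start or stop date and uses the result to determine prior or concomitant status, so the text is ambiguous for that pattern. The contradiction survives either reading, because there both dates are missing.

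A default to concomitant can be defended as cautious; SAP Section 13.1 resolves missing adverse event severity and relationship in that spirit. This does not explain the opposite default for baseline status on the same test.

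A reader might go further and infer that past phenytoin or phenobarbital without dates would move subjects between subgroups, create apparent breaches of exclusion criterion 6, or inflate AED exposure by years. The documents do not support this. SAP Section 9.2 does not derive subgroups from imputed dates. Protocol deviations come from the monitoring organisation's tracking system (SAP Section 11.2). Duration of AED use enters no planned summary of concomitant AEDs, and SAP Section 11.4 lists AED exposure as recorded. Nor do the documents say that stop dates of previously failed AEDs are the ones usually missing.

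**Conclusion.** The concern holds in a narrow form. For an AED that is not ongoing and has neither date, the stated rules produce a status that SAP Section 11.5 rules out. This is an error in the rules as written, not missing detail. Two neighbouring patterns lack an outcome in one rule set or the other.

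The effect is limited to the descriptive baseline and concomitant AED tables, including the baseline AED count. Its total size cannot be computed, because the number of affected records is not given; the 5-point and 0.1-point figures are per record and assume the subject is not already counted for that drug. Subgroup assignment, protocol deviations and exposure duration are not shown to be affected. It is worth correcting because the tables should agree and the correction is cheap.

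**What to change.** In Appendix 2, set baseline and concomitant status together, by one rule, for any AED that is not ongoing, whose start is missing or before first dose, and whose stop year is unknown (stop wholly missing, or day and month only):

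- If the AED administration records show it taken at first dose, it is both baseline and concomitant.
- If they show it taken only after first dose, it is concomitant only.
- If they show no use at or after first dose, it is neither.

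Exempt these AED records from general rule 3. This closes the contradiction and both gaps.

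The source is already planned: SAP Section 8.2.2 states "Concomitant AED administration since last visit will be recorded on the eCRF page". That sentence is all the documents say about the page, so the sponsor should confirm that it carries information beyond the missing start and stop dates. Where it does not, the last line of the rule still gives one consistent answer.

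The cost is revised wording and a merge with data already collected; SAP Section 4 allows revision before database lock. The small downside is that AEDs and other medications would then follow different rules for a missing stop date.

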13.1 Analysis of Adverse Events (treatment -emergent, non-serious, serious, and deaths)

Adverse events will be coded to a Medical Dictionary for Regulatory Activities Terminology (MedDRA) version 20.0 or later version available at the time of data cut-off. Verbatim description and the MedDRA System Organ Class (SOC) and Preferred Term for all adverse events will be contained in the subject data listings of the clinical study report.

For adverse events with partial start date (i.e., with only month and year are recorded), the following imputation rule will be applied: 15th of the month or fist dose date which one comes later. The imputed date will be used to derive TEAE analysis flag. The actual collected date will be displayed in all AE data listings.

All reported adverse events (regardless of treatment-emergent or not) will be included in a by- subject adverse event listing, with separate by-subjects listings for adverse events and serious adverse events reported for screen failures.

Only treatment-emergent adverse events will be included in summary tables.

Treatment emergent adverse events (TEAE) are defined as AEs with onset after the start of study medication, up to last dose date of study medication + 14 days (or analysis cut-off date whichever comes first), or onset before study medication and worsened after starting study medication, up to last dose date of study medication + 14 days (or analysis cut-off date whichever comes first).

An adverse event is regarded as related to study medication if the relationship to study medication is definite, probable, or possible. Adverse events with missing

relationship will be assumed to be treatment related. Adverse events with missing severity will be assumed to be severe in order to perform the most conservative statistical analysis.

Severe adverse events and adverse events related to treatment will be summarized overall and by safety evaluable subgroups.

TEAE Incidence will be computed as number of subjects with AE/ number of subjects in each reporting group (%).

Incidence of TEAEs leading to study drug discontinuation will report only TEAEs with Action Taken = study drug discontinuation.

In TEAE summary tables, system organ classes (SOCs) will be presented in alphabetical order and preferred terms within each SOC will be presented in descending order of frequency in overall YKP3089 group within each SOC, unless specified otherwise.

The planned summary of adverse events tables are listed below:

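### SAP Appendix 2, rules (3) and (4), can count an AED added on study as a baseline AED when its start date is incomplete and compatible with a start on or before first dose

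*SAP*

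**What the plan says.** SAP 11.5 gives the definition: "Baseline AED medications are defined as AED medications that started prior to and are ongoing at the time of the first dose". Appendix 2 repeats it. The result feeds the summaries of baseline AED use and of the number of baseline AEDs per subject (categories 0, 1, 2 and above 2, plus mean, SD, median and range).

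The Baseline AEDs part of Appendix 2 then sets four rules for incomplete dates:

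- Rule (1): an AED with neither a start nor a stop date is not a baseline AED.
- Rule (2): for an AED marked prior, not ongoing and with a partial end date, the known parts of the end date are compared with first dose.
- Rule (3): for an AED that the eCRF does not mark as prior, "the following rules will be considered if start dates are missing or have partial dates". With month and year known, "impute the missing day is the 1st day of the corresponding month". With only the year known, "impute the missing day and month to the 1st of January of the corresponding year". With nothing known, the start becomes the start of screening.
- Rule (4): if the imputed start is after first dose, the AED is neither prior nor baseline. If it is on or before first dose, the AED becomes prior "and will be evaluated as potential Baseline AED", and the end date decides under rule (2).

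**The concern.** Rule (3) applies only to AEDs that the site did not mark as prior, yet it gives them the earliest date that the record allows. Rule (4) then relies on that imputed date instead of on the missing flag. For an AED truly added after first dose, the error can go only one way: it raises the baseline count.

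Such additions are expected. Protocol Table 8 lets the cohort on other AEDs change concomitant AEDs during titration, and Table 9 lets all cohorts do so in maintenance. The baseline AED count tells the reader how heavily treated the subjects were at entry, and drugs added later do not belong in it.

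**Working it through.** The SAP gives no figure for this point, so there is none to reproduce. The check applies the rules as written to an AED that truly started after first dose and is not marked prior.

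**Worked cases, first dose 15 March 2017**

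| Recorded start | True start | Stop date | Imputed start | Result |
|---|---|---|---|---|
| March 2017 | 25 March 2017 | ongoing | 1 March 2017 | baseline (wrong) |
| April 2017 | 10 April 2017 | ongoing | 1 April 2017 | not baseline |
| 2017 | 1 September 2017 | ongoing | 1 January 2017 | baseline (wrong) |
| 2018 | 1 February 2018 | ongoing | 1 January 2018 | not baseline |
| missing | 1 September 2017 | 10 January 2018 | start of screening | baseline (wrong) |
| missing | 1 September 2017 | ongoing | see below | depends on rule (1) |

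Rule (2) does not cover ongoing AEDs, so these fall back on the general definition and count as in use at first dose. In the last row, the AED is excluded if the empty stop date of an ongoing drug counts as missing under rule (1), and is baseline if it does not. Appendix 2 leaves the end date of ongoing medications empty but does not say which reading applies.

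**Share misclassified among partial-date records.** Assumptions: first dose uniform over a 365-day year; true start uniform over days 1 to H after first dose; AED ongoing and not marked prior.

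Month and year known: the record is misclassified if the start falls in the month of first dose. The mean number of days left in that month is the sum of m(m−1)/2 over the 12 months, divided by 365, where m is the month length:

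(7×465 + 4×435 + 378)/365 = 5,373/365 = 14.72 days. The share is 14.72/H.

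Year only: the record is misclassified if the start falls in the year of first dose. With r days left in the year (0 to 364), the share is the mean of min(r, H), divided by H:

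- H = 84: (3,486 + 84×281)/365 = 27,090/365 = 74.2; 74.2/84 = 88.4%.
- H of 365 or more: the mean of r is 182, so the share is 182/H.

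| AED added within | Month and year known | Year only |
|---|---|---|
| 84 days (titration) | 17.5% | 88.4% |
| 365 days | 4.0% | 49.9% |
| 730 days | 2.0% | 24.9% |
| 1,095 days | 1.3% | 16.6% |

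**Is a pre-dose start plausible for the month-only records?** Inclusion criterion 6 requires stable doses of 1 to 3 AEDs for at least 3 weeks before Visit 2, and first dose is on the day of Visit 2 or the next morning. If Visit 2 falls on days 1 to 21 of a month, an AED begun earlier in that month has been taken for at most 20 days and does not fit the criterion. For most month-only records sharing the month of first dose, rule (3) thus prefers a start that conflicts with eligibility over one that does not.

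**The case against.** A reader might infer that every unflagged AED with an incomplete start date becomes baseline. The rules do not say that. The first branch of rule (4) excludes any partial date whose imputed value is after first dose. On a plain reading, rule (1) excludes a still-ongoing AED with no start date. Both limits stand.

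The eCRF is not among the documents, so an absent prior flag cannot be read as the site's positive statement that the drug was new. Rules (3) and (4) may be meant to catch long-standing AEDs that were not flagged. Visits are two weeks apart early on, so vague dates are more likely for old drugs than for new ones. This has force for year-only dates, where a start months before first dose can satisfy criterion 6. It has little force for month-only dates, for the reason shown in the working.

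SAP 13.1 dates a partial adverse event start to the "15th of the month or fist dose date which one comes later". That shows that a floor at first dose is familiar to the authors. It is not a standard for AEDs, because there the floor makes events treatment-emergent, which is the cautious choice for safety.

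It is also tempting to say that the rule would show subjects above the entry limit of 3 AEDs. The top category of the table is above 2, so a move from 3 to 4 changes only the mean and maximum, and nothing in the SAP judges eligibility from this table.

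Finally, refusing baseline status to every unflagged AED would be worse than the present rule. An ongoing AED recorded as started in 2010 would be dropped against its own year, while rules (3) and (4) classify it correctly.

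**Conclusion.** The point holds in a limited form. Rules (3) and (4) count an on-study AED as baseline when its partial start shares the month or year of first dose, or when its start is missing and a stop date on or after first dose is recorded. The documents do not support the wider reading that any incomplete start, or every missing start, has this effect.

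Among month-only records the share is about 18% for AEDs added within 84 days. Among year-only records it is 50% to 88% for those added within 365 or 84 days. Both fall for later additions and rest on the uniform assumptions above. They are shares of the incomplete records for AEDs truly added on study. The documents do not say how many there are, and the number is probably small.

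The damage is confined to descriptive baseline AED tables. SAP 10.1 plans no inferential analysis, and under SAP 11.5 an AED in use at first dose or started later is concomitant either way. This is a minor point, worth making because the rule as stated biases the count upward and is easily corrected.

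**What to change.** Amend Appendix 2 as follows:

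- In rule (3), for an AED not recorded as prior whose known date parts do not place the start before first dose (same month or year as first dose, or start missing), impute the start to the later of the rule (3) date and the day after first dose, and do not count the AED as baseline. The stop date is one of the known parts: a record that stopped on or before first dose cannot be given a later start, so leave it to rule (4) with a query.
- Where the known parts clearly precede first dose, keep rule (4) as written and query the site about the flag.
- In rule (1), state whether an ongoing AED counts as having a missing stop date.

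The cost is a few lines of SAP text, a small programming change and a few queries. The downside is that a pre-existing AED that the site failed to flag, and either dated only to the month or year of first dose or left without a start date, would be left out unless a query resolves it. Querying these records too, before database lock, would limit that loss.
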